1.5. Randomization and Blinding

Central randomization will be implemented in this study. At the start of the double-blind phase, subjects will be randomly assigned to one of two treatment groups based on the first of

two computer-generated randomization schedules prepared before the study by, or under the supervision of the sponsor. The randomization will be balanced by using randomly permuted blocks. Presence of comorbid major depressive disorder (MDD) and country will be used as stratification factors.

Blinded treatment will be used to reduce potential bias during data collection and evaluation of clinical endpoints.

The investigator will not be provided with randomization codes. The codes will be maintained within the IVRS/IWRS, which has the functionality to allow the investigator to break the blind for an individual subject.

Data that may potentially unblind the treatment assignment (e.g., study medication plasma concentrations, plasma biomarkers) will be handled with special care to ensure that the integrity of the blind is maintained and the potential for bias is minimized. This can include making special provisions, such as segregating the data in question from view by the investigators, clinical team, or others as appropriate until the time of database lock and unblinding.

Under normal circumstances, the blind should not be broken until all subjects have completed the study and the database is finalized. Otherwise, the blind should be broken only if specific emergency treatment/course of action would be dictated by knowing the treatment status of the subject. In such cases, the investigator may in an emergency determine the identity of the treatment by contacting the IVRS/IWRS. It is recommended that the investigator contact the sponsor or its designee if possible to discuss the particular situation, before breaking the blind. In the event the blind is broken, the sponsor must be informed as soon as possible. The date, time, and reason for the unblinding must be documented in the appropriate section of the case report form (CRF), and in the source document. The documentation received from the IVRS indicating the code break must be retained with the subject's source documents in a secure manner.

Subjects who have had their treatment assignment unblinded should continue to return for required follow up evaluations.

In general, randomization codes will be disclosed fully only if the study is completed and the clinical database is closed. However, if an interim analysis is specified, the randomization codes and, if required, the translation of randomization codes into treatment and control groups will be disclosed to those authorized and only for those subjects included in the interim analysis.

2. GENERAL ANALYSIS DEFINITIONS

2.1. Treatment Groups

Tables summarizing data in the double-blind treatment phase will have columns for ‘Placebo’ and ‘JNJ-42165279 25 mg’.

Subjects who received an incorrect treatment will be analyzed under the treatment they were randomized to.

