## 9.5.3. Pharmacokinetic Parameters

PK analyses of the plasma concentrations will be undertaken to estimate peak plasma concentration and systemic exposure of JNJ-42165279. Based on the individual plasma concentration-time data, if sufficient data are available, the following PK parameters of JNJ-42165279 will be estimated at steady state in subjects receiving a dose of JNJ-42165279 using population PK modeling:

C max	maximum plasma concentration
t max	time to reach the maximum plasma concentration
$AUC_{\tau}$	area under the plasma concentration-time curve from 0 to $\tau$ hours post dosing (time $\tau$ is the dosing interval)

The parameters of interest for the statistical analysis will be the log-transformed estimated dose normalized AUC and  $C_{max}$ . All ratios will be calculated as differences of least square means of the appropriate model on the log-scale, and will be presented after back-transformation to the original sale with the corresponding 90% confidence intervals (CIs).

Based on the individual plasma concentration-time data, using the actual dose taken and the actual sampling times, PK parameters and exposure information of JNJ-42165279 will be derived using population PK modelling. Baseline covariates (e.g., body weight, age, sex, CrCL, race) may be included in the model, if relevant.

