## 11.4. Safety Analysisa

All subjects receiving at least one dose of study drug will be included in the safety analysis. All safety analyses will be performed based on the safety analysis set, which will include all randomized subjects who receive at least 1 dose of study drug.

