2.5.4. Safety Analysis Set

The Safety analysis set is defined as all randomized subjects who received at least one dose of study medication (either placebo or JNJ-42165279). Screen failures and randomized subjects who received no double-blind study medication will be excluded from the Safety analysis set.

The Safety analysis set is the analysis set for the safety analyses.

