7. BIOMARKERS

Biomarker analyses will be based on the safety analysis set, which will include all randomized subjects who receive at least one dose of study medication (either placebo or JNJ-42165279).

During the study, the following biomarker evaluations will be performed at Day 1, Day 28 and Day 84/ end of withdrawal visit: plasma concentrations of FAAs (AEA, PEA and OEA).

Descriptive statistics of actual values and changes and percent changes from baseline for concentrations of AEA, PEA and OEA at each scheduled time point and endpoint will be provided by treatment group (mean, SD, median and range). A mean-SE plot over time will be presented by treatment group, and results will be listed.

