8. SAFETY

All safety analyses will be based on the safety analysis set, which will include all randomized subjects who receive at least one dose of study medication (either placebo or JNJ-42165279).

All safety data will be listed for the subjects in the safety analysis set.

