8.2. Adverse Events

The verbatim terms used in the CRFs by the investigator to identify adverse events (AEs) will be coded using the current Medical Dictionary for Regulatory Activities maintained by the sponsor.

Therapeutic reach is the number of days after the last dose intake that a subject is still considered to be potentially affected by study drug. For JNJ42165279, therapeutic reach is defined as 4 days. AEs will be summarised using the therapeutic reach. Therapeutic reach will only be applied to the end of double-blind treatment period or to subjects who discontinue.

A treatment-emergent AE (TEAE) is an event that is new in onset or increased in severity following treatment initiation. Any event with a start date and time after the first dose intake will be considered treatment-emergent. An event that starts prior to and ends after the initiation of study medication will be considered treatment-emergent only if the severity increases after the start of medication. An event that starts in the follow up period but within the therapeutic reach of 4 days will be considered treatment-emergent. Adverse events with onset date during the follow-up phase outside the therapeutic reach of 4 days will be summarized separately.

The number (%) of subjects with TEAEs will be summarized by system organ class and preferred term for each treatment group. A summary will be created for the most common TEAEs ($\geq 5\%$ incidence in either treatment group). In addition, TEAEs will be summarized by severity and relationship to study drug for each treatment group by system organ class and preferred term. For the summaries of AEs by severity/relationship to study drug, the observation with the most severe occurrence/closest relationship to study drug will be chosen if there is more than one incident of an adverse event reported during the treatment phase by the subject.

TEAEs will also be summarized by sex, by country, and by enrollment prior to/after study suspension.

Serious AEs (SAEs) and TEAEs that lead to study discontinuation will be summarized separately by treatment group, system organ class and preferred term.

Treatment-emergent headaches, TEAEs related to liver function test abnormalities and TEAEs of special interest (diplopia, vision impairment, gait disturbance, severe headache) will be presented graphically over time for each individual subject.

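### SAP 2.1 groups wrongly treated subjects by randomised arm in the safety and biomarker tables as well as the efficacy tables, so any misdosed subject's events and FAA values would be tabulated under the wrong product

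*SAP*

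**What the plan says.** SAP 2.1, within Section 2 on general definitions, sets the layout first: "Tables summarizing data in the double-blind treatment phase will have columns for" placebo and JNJ-42165279 25 mg. The next sentence gives the assignment rule: "Subjects who received an incorrect treatment will be analyzed under the treatment they were randomized to". No analysis set or type of endpoint is excepted.

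The later sections inherit the rule:

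- SAP 2.5.4: "The Safety analysis set is defined as all randomized subjects who received at least one dose of study medication (either placebo or JNJ-42165279". This settles membership and says nothing about grouping.
- SAP 8: "All safety analyses will be based on the safety analysis set". SAP 8.2 adds: "The number (%) of subjects with TEAEs will be summarized by system organ class and preferred term for each treatment group". The laboratory, vital-sign and ECG summaries in SAP 8.3 to 8.5 are also by treatment group.
- SAP 7: "Biomarker analyses will be based on the safety analysis set". AEA, PEA and OEA are summarised by treatment group.
- Protocol 11.4 describes the same safety set, "which will include all randomized subjects who receive at least 1 dose of study drug", and does not mention grouping.

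The one place where actual intake governs the analysis is the population PK model in Protocol 9.5.3, which works "using the actual dose taken and the actual sampling times".

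**The concern.** Grouping by randomised arm is right for the efficacy comparison, because it preserves what randomisation delivers. Safety and pharmacodynamic summaries ask a different question: what happened to people who took the drug. Under SAP 2.1, a placebo-randomised subject who took active tablets has any resulting adverse event, transaminase rise, QTc change or FAA rise counted under placebo. A subject randomised to JNJ-42165279 who took placebo contributes drug-free observation to the active column.

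Safety and tolerability is the first secondary objective. The protocol records mild reversible transaminase elevations at 100 mg in Phase 1 (Protocol 1.1 and 16.1), so the placement of even one liver case could affect how a table is read. The plasma FAAs are an exploratory measure of peripheral pharmacological activity.

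**Working it through.** The plan gives no figure to reproduce. The check is of the text first, then of the size of one error.

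**Text.** Is there an as-treated rule anywhere that overrides SAP 2.1? SAP 2.5.4, 7 and 8 and Protocol 11.4 contain none. Protocol 9.5.3 uses the actual dose, but only for population PK. SAP 4.4 lists study drug administration by subject without changing the table columns. So SAP 2.1 governs.

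**Inputs.**
- Arm size: 137 randomised 1:1 (Protocol 3.1), and 137/2 = 68.5, taken as 68. The SAP's own total of 122 would give 61.
- AEA response: mean peak plasma AEA 5.5 to 10 times predose after single doses of 25 to 100 mg (Protocol 1.1), read as multiples. The rise is then (5.5 − 1) × 100 = 450% to (10 − 1) × 100 = 900%.
- Number of misdosed subjects, k: not in the documents. Assumed to be 1 to 3 for illustration.

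**Adverse event rates.**
- One event in the wrong column: 1/68 = 1.5 points per arm (1/61 = 1.6).
- Difference, with denominators held fixed: 2 × 1.47 = 2.9 points.
- If the subject moves with the event, the denominators become 67 and 69. Starting from 7 events in each arm, the difference becomes 8/69 − 6/67 = 11.6% − 9.0% = 2.6 points. So 2.9 is near the maximum.
- For k = 1 to 3, up to 1/68 = 1.5% to 3/68 = 4.4% of the placebo column could carry drug-caused events.
- A reporting threshold can be crossed. SAP 8.2 summarises TEAEs at 5% or more in either group. Three events in 68 on active is 4.4%, which is left out. Adding one misdosed subject with that event gives 4/69 = 5.8%, which is included.

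**Direction.** Let a fraction f of the placebo column have taken active drug, with true rates pA and pP. The expected placebo-column rate is (1 − f)pP + f·pA, so the expected difference is (1 − f)(pA − pP). With assumed rates of 20% and 10%, a true 10.0-point difference reads as 9.85 points for k = 1 and 9.56 for k = 3. Misdosing in the other direction shrinks it in the same way. This is an expectation and does not fix the direction for any one subject.

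**AEA.** Assume no change on placebo and one misdosed placebo subject sampled at peak.
- Added to the placebo mean percent change: 450/68 = 6.6 to 900/68 = 13.2 percentage points, so the mean reads 1.07 to 1.13 times baseline.
- With k = 3: 1 + 4.5 × 3/68 = 1.20 to 1 + 9 × 3/68 = 1.40 times baseline.
- If only 85% contribute a sample (68 × 0.85 ≈ 58), one subject adds 450/58 = 7.8 to 900/58 = 15.5 points.

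The fold values lean high. They are peaks and span 25 to 100 mg, whereas the trial uses 25 mg. Protocol 9.1.3 lets Day 28 and Day 84 assessments fall before or after the dose. Bottles hold 31 tablets and are dispensed at Day 1, Week 4 and Week 8, so a single wrong Week 4 bottle could miss both post-baseline FAA samples.

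**The case against.** The strongest reply is that nothing has gone wrong. No misdosed subject is reported, allocation is central, there is one tablet strength, and kits are packed per subject. The safety and FAA outputs are descriptive and drive no test. A misdosed subject would also be traceable: medication errors are recorded in the CRF (Protocol 12.2), drug administration, deviations and all adverse events are listed, and liver tests and selected events are graphed by subject. FAA results are listed and summarised with median and range, and FAAs are plotted against measured drug concentration (Protocol 11.6).

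All of that is correct, and it limits the importance of the point. It does not change which column the subject occupies. Traceability lets a careful reader undo the misattribution but does not prevent it. Nor is this a missing detail, since the SAP foresees wrong treatment and prescribes the assignment.

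Some stronger inferences are not supported:

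- That drug reactions have already been counted under placebo. The documents show no such case.
- That the error always dilutes. A subject randomised to JNJ-42165279 who took placebo and had an unrelated event would add to the active column. Dilution holds only in expectation.
- That the FAAs are the trial's proof of target engagement. They are exploratory, and the dose rationale (Protocol 3.2) also rests on PET occupancy, white-cell FAAH activity and CSF concentrations.
- That the SAP contradicts the protocol. Protocol 11.4 is silent on grouping.

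**Conclusion.** The point holds as a conditional defect. As written, SAP 2.1 puts a wrongly treated subject's safety and FAA data in the column of the product that subject was assigned, and no other section corrects this. If no subject takes the wrong product, no table changes.

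If one does, a single event shifts each arm's rate by about 1.5 points and the difference by up to about 2.9. The placebo mean AEA percent change rises by at most about 7 to 13 points, taking 68 contributing subjects and peak response. That is small beside the 450% to 900% rise assumed for active drug, so the biomarker conclusion would be unlikely to turn on one subject. The safety side matters more: the expected bias is toward showing less difference from placebo, and rare events are read case by case. The number of misdosed subjects is an assumption throughout.

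**What to change.** In SAP 2.1, limit the as-randomised sentence to the ITT efficacy analyses and the All Randomized summaries. Then add:

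- Safety tables are presented by treatment actually received.
- A rule for subjects who took both products, written before the final unblinding. One example is to count them under JNJ-42165279 for safety and flag events that began before the first active dose.
- FAA summaries are grouped by the product being taken at each sampling visit. Applying an any-active-dose rule here would be a mistake: a placebo subject with one wrong mid-study bottle would bring placebo-level samples into the active mean.
- A listing of all affected subjects, with the product taken and the dates.

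The same edit should say which grouping the Safety-set demographic and exposure tables follow.

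The cost is an actual-treatment variable, by visit for the biomarkers, and a small amount of programming. No additional subjects are needed, and because Protocol 11.4 does not address grouping, the change does not conflict with it. Fixing the rule in advance also avoids choosing a subject's column after seeing the events.

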2.2. Pooling Algorithm for Analysis Centers

No pooling of centers will be carried out.

2.3. Other General Definitions

2.3.1. Study Day 1 or Day 1

Study Day 1 or Day 1 refers to the first day of double-blind study drug administration. All efficacy and safety assessments at all visits will be assigned a day relative to this date.

2.3.2. Study Day or Relative Day for a Visit

Study day or relative day for a visit is defined as:

- Visit date - Date of first dose of study medication (date of Day 1) +1, if visit date is \geq date of Day 1
- Visit date - Date of Day 1, if visit date is $<$ date of Day 1

By definition there is no ‘Day 0’.

2.3.3. Baseline

Baseline is defined as the last non-missing observation prior to first dose of study drug.

2.3.4. End Point

End point is defined as the last non-missing post-baseline observation during the Double-Blind treatment phase (defined in Section 2.3.5).

2.3.5. Analysis Phases

All data collected from the Baseline visit to the End Point/Early Withdrawal visit (inclusive) will be assigned to the Double-Blind Treatment analysis phase. Data collected prior to the Baseline visit will be assigned to the Screening analysis phase, and data collected after the End Point/Early Withdrawal visit will be assigned to the Post Treatment analysis phase.

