### 9.1.3. Double-Blind Treatment Phasea

#### Day 1

Subjects who successfully complete the screening examination will visit the clinical site on Day 1 during the morning hours.

Prior to dosing the following (baseline) assessments will be performed:

- Body weight
- 12-lead ECG recording (triplicate)

<sup>a This section has been amended per Amendments INT-1, 2 and 3.

- Body temperature
- Supine and standing vital signs (systolic and diastolic blood pressure and pulse)
- C-SSRS
- Clinical safety laboratory assessments under fasted conditions, when feasible (including hematology, serum chemistry, coagulation and urinalysis)
- Blood sample collection for pharmacogenomics
- Blood sample collection for FAAs
- Urine drug screen
- Alcohol screen (in blood)
- All women: Urine pregnancy test
- Review of inclusion and exclusion criteria
- Randomization
- Dispense JNJ-42165279/placebo
- LSAS
- HDRS17 using the SIGH-D
- SIGH-A
- SDS
- GAD-7
- SHAPS
- MOS Sleep-R
- Q-LES-Q
- Behavioral guidance from the investigator
- Record adverse events and concomitant medication

Study medication will be dispensed (incl. drug accountability) and administered as outlined in Section 6, Dosage and Administration. Subjects will self-administer their study medication q.d. as instructed.

On Day 1 dosing will not be time limited and will be performed following completion of the baseline (predose) assessments, which will be witnessed by designated study-site personnel at the study sites.

During the double-blind treatment period, following Day 1, subjects will return to the investigational site at regular time points as indicated in the Time and Events Schedule and further described below.

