2.5.3. Intent-to-Treat (ITT) Analysis Set

The ITT analysis set is defined as all randomized subjects who received at least one dose of study medication (either placebo or JNJ-42165279), and have at least one assessment in the double-blind treatment phase on any of the efficacy parameters. Subjects who withdrew early from the study at the time of study suspension will not be included in the ITT analysis set (7 placebo subjects, 8 JNJ-42165279 subjects). Subjects who had already completed the study at the time it was suspended, however, will be included in the ITT set (9 placebo subjects, 9 JNJ-42165279 subjects).

The ITT analysis set is the analysis set for the efficacy analyses.

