male	0.24	0.55
female	0.28	0.5

Graphical presentations will be created for the following liver function tests: alanine aminotransferase, aspartate aminotransferase, albumin, bilirubin, alkaline phosphatase, gamma glutamyl transferase. Liver function test results standardized to the upper limit of normal (based on central laboratory ranges) will be graphically presented over time for each subject. The incidence of liver function tests above the central laboratory normal limit will be presented by treatment group at each scheduled time point, at endpoint, and at any time during the double-blind treatment phase.

Graphical presentations will also be created for prothrombin international normalized ratio results.

Clinical laboratory tests that meet the criteria for abnormal and markedly abnormal will be listed by subject.

Results on urine drug screen, alcohol screen and pregnancy test will be presented in a listing.

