Table 8: Abnormal limits for orthostatic parameters

Vital Signs Parameter	Outside of normal limit if difference (Standing minus supine)
(1) Pulse (bpm)	> 15 bpm
(2a) Systolic blood pressure (mmHg) (SBP)	< - 20 mmHg
(2b) Diastolic blood pressure (mmHg) (DBP)	< -10 mmHg

Orthostatic hypotension requires that conditions (1) and [(2a) or (2b)] are met.

For subjects who are unable to stand and have the vital signs measured in a sitting or supine position instead of the standing position, the difference between standing and supine value will remain missing.

Frequency table of the occurrence of orthostatic hypotension at each scheduled time point and endpoint and at any time during the double-blind treatment phase will be presented by treatment group. Listings will be provided for subjects who have orthostatic hypertension.

Physical examination abnormalities and neurological examination results will be listed.

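### SAP 2.3.5 puts the pre-dose Baseline visit in the Double-Blind Treatment phase, so two any-time safety counts (liver tests above normal, orthostatic hypotension) include pre-dose-only findings

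*SAP*

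**What the plan says.** - **Phase definition.** SAP 2.3.5: "All data collected from the Baseline visit to the End Point/Early Withdrawal visit (inclusive) will be assigned to the Double-Blind Treatment analysis phase". Table 2 (SAP 2.4) repeats this. For clinical laboratory assessments, vital signs and the LSAS, the Baseline row (day 1 or earlier) is labelled as double-blind treatment.
- **Baseline is pre-dose.** SAP 2.3.3: "Baseline is defined as the last non-missing observation prior to first dose of study drug". Protocol 9.1.3 opens its Day 1 list with "Prior to dosing the following (baseline) assessments will be performed". That list includes the safety laboratory tests and the supine and standing vital signs.
- **Liver table.** SAP 8.3: "The incidence of liver function tests above the central laboratory normal limit will be presented by treatment group at each scheduled time point". The same sentence adds two further counts, one for endpoint and one over the whole phase, the latter worded as "at any time during the double-blind treatment phase".
- **Orthostatic table.** SAP 8.4 plans a "Frequency table of the occurrence of orthostatic hypotension at each scheduled time point and endpoint and at any time during the double-blind treatment phase". The criterion in Table 8 is standing minus supine at a single visit, with no reference to baseline.
- **ITT set.** SAP 2.5.3 requires dosed subjects to "have at least one assessment in the double-blind treatment phase on any of the efficacy parameters".

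**The concern.** An any-time count over the treatment phase is normally read as what happened on treatment. Here the phase opens before treatment does, and these two counts carry no condition that removes pre-dose values. An abnormality that cleared after Day 1 and never returned would still be reported as occurring during treatment.

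The drug cannot have caused a pre-dose finding, and randomisation makes such findings equally likely in both arms. Counting them raises both percentages and moves their ratio toward 1. The liver table is the more important of the two. Protocol 16.1 names reversible mild transaminase elevation as the Phase 1 safety signal, and Protocol 1.1 describes elevations of up to 2.5 times the upper limit of normal (ULN). The markedly abnormal rule in SAP Table 5 starts above 3 times ULN for ALT and AST. An elevation of the Phase 1 size would therefore show in the above-limit count but not in the markedly abnormal count.

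**Working it through.** **Step 1: does the wording admit pre-dose values?**

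| Output | Condition in the SAP | Pre-dose Baseline value counted? |
|---|---|---|
| Markedly abnormal laboratory values (8.3) | Post-baseline, glossed as after the start of study medication | No |
| Vital-sign abnormalities (Table 7) | Post-baseline value with a change from baseline | No |
| End Point (2.3.4) | Post-baseline | No |
| Treatment-emergent adverse events (8.2) | Onset after first dose, or worsening after it | No |
| Liver tests above normal, any time (8.3) | Double-blind phase only | Yes |
| Orthostatic hypotension, any time (8.4) | Double-blind phase only | Yes |

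The End Point definition asks for a value that is both post-baseline and within the double-blind phase. The phase label therefore does not by itself exclude pre-dose data.

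**Step 2: can such cases occur?** Yes. Exclusion criterion 8 bars liver tests above 2 times ULN, so values between 1 and 2 times ULN can be present before dosing, subject to review with the sponsor. Supine and standing readings are both taken before the Day 1 dose, so the Table 8 criterion can be evaluated then.

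**Step 3: how large is the effect?** The plan states no figure to reproduce and gives no background rates, so every rate below is an assumption. The visit counts come from Table 2: six post-dose laboratory draws (Weeks 2, 4, 6, 8, 10, 12) and five post-dose vital-sign visits (Weeks 1, 2, 4, 8, 12).

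Model: a latent normal value with a subject random intercept u and within-subject correlation r. The threshold z gives prevalence p at an untreated draw, and the drug shifts post-dose values by s. The chance that one post-dose draw is abnormal, given u, is q_s(u) = P[N(0,1) > (z − s − √r·u)/√(1 − r)]. Then, averaging over u:

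- A = E[1 − (1 − q_s)^6], abnormal at some post-dose draw
- B = E[q_0·(1 − q_s)^6], abnormal before dosing only
- Count as written = A + B; count from post-dose values = A

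With p = 5% (z = 1.645) and r = 0.7, by numerical integration:

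| | A | B | A + B |
|---|---|---|---|
| Placebo (s = 0) | 14.754% | 1.100% | 15.854% |
| Drug (s = 0.4) | 27.131% | 0.375% | 27.506% |

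- Risk ratio, post-dose values: 27.131 / 14.754 = 1.84. As written: 27.506 / 15.854 = 1.735.
- Risk difference, post-dose values: 27.131 − 14.754 = 12.4 points. As written: 27.506 − 15.854 = 11.7 points.

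Simulation of 400,000 subjects gives about 1.83 to 1.72 for the ratio and 12.2 to 11.5 points for the difference. The two methods agree within simulation error.

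**Ranges.**
- Liver tests, p = 2.5–10% and r = 0.5–0.85: pre-dose-only subjects are 4–10% of the placebo subjects counted per analyte, or 0.4–2.5 percentage points. Per 61 subjects this is 0.004 × 61 = 0.2 to 0.025 × 61 = 1.5. The risk difference changes by about 0.3 to 1.4 points.
- Orthostatic hypotension, p = 2–10% and r = 0.2–0.4: 10–15% of counted subjects are pre-dose only, about 0.7 to 2.7 per 61.

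**The case against.** The strongest reply is that the liver signal is well covered elsewhere. SAP 8.3 has by-arm shift tables from baseline to each visit and endpoint, markedly abnormal counts on post-baseline values, per-subject plots standardised to ULN, and listings. SAP 8.2 plots liver-related adverse events by subject. No hypothesis test uses either affected table. Intent can also be inferred, since Protocol 11.4 treats adverse events with onset in the double-blind phase as treatment-emergent. Most of this stands, and it limits the point to one column in each of two descriptive tables. It does not remove the point: the shift tables are not any-time counts, and a programmer filtering on the phase variable would follow 2.3.5 exactly.

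Four stronger readings are tempting, but the documents do not support them.

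- *The plan hides the liver signal.* It does not. The outputs just listed are unaffected, as are the by-visit and endpoint columns of the liver table itself.
- *The dilution is large.* Assume 15% against 5% new onset, so a ratio of 3.0, and add a baseline-abnormal share b to both arms. At b = 15% the ratio is (0.15 + 0.85 × 0.15) / (0.15 + 0.85 × 0.05) = 27.75 / 19.25 = 1.44. That compares new onset in baseline-normal subjects with an any-time count, which is a different estimand. A subject high at baseline and again after dosing is counted with or without the Baseline visit. In the model above, 55–90% of baseline-high placebo subjects are also high after dosing.
- *The primary analysis is compromised through the ITT definition.* The Day 1 LSAS does meet the 2.5.3 condition literally. A subject with no later efficacy data contributes nothing to the MMRM, however, and End Point is already post-baseline. Only set counts and the baseline summary change.
- *The whole phase must be redefined.* That would alter the Baseline row of every parameter in Table 2, which is broader than two missing qualifiers require.

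**Conclusion.** The point holds on the wording. SAP 2.3.5, Table 2 and 2.3.3 together place pre-dose data in the phase over which 8.3 and 8.4 take their any-time counts, and neither count has the post-baseline condition that the SAP writes elsewhere. As written, both arms are modestly inflated and the drug/placebo ratio is pulled toward 1, in the any-time column only.

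The size is illustrative: a risk ratio of about 1.83 becoming 1.72, with the risk difference falling by under one point in that setting. It rests on assumed prevalence, correlation and drug shift, and on the phase rule being programmed literally. The change is still worth making, because the error runs toward masking a drug effect on the named safety signal and the column label is wrong whatever the size.

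**What to change.** - **SAP 8.3 and 8.4:** state that the any-time counts of liver tests above normal and of orthostatic hypotension use post-baseline values only, meaning values after the first dose.
- **SAP 8.3, optional:** show the any-time liver count separately for subjects within and above the limit at baseline, since the shift tables give this only by visit and endpoint.
- **SAP 2.5.3, for consistency:** require at least one post-baseline efficacy assessment.

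SAP 2.3.5 and Table 2 can stay as they are. The cost is a few words and one programming condition, with no new data. The reported any-time counts become slightly smaller, and the ITT count may fall by any subject who has only pre-dose efficacy data.
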